Research protocol

1. Research background

In the therapeutic landscape of congenital heart disease (CHD), traditional pain management focuses primarily on pharmacotherapy, particularly in postoperative pain management. This usually includes the use of opioids and NSAIDs to reduce pain in children. However, these drugs often carry adverse reactions and side effects, especially in pediatric children, such as respiratory depression, dependence, digestive discomfort, etc. Additionally, pharmacotherapy may not fully address all aspects of postoperative pain management, especially in terms of emotional and psychological coping strategies. In terms of non-pharmacological care interventions, there have been some studies that suggest that environmental control, physiotherapy (e.g., massage and hot and cold therapy), cognitive behavioural therapy, relaxation training, and other psychosocial interventions may have a positive effect on reducing postoperative pain. These methods are often seen as adjunctive treatments and are used to complement traditional pharmacotherapy. Currently, non-pharmacological pain management in children with congenital heart disease is understudied, and there are no clear, evidence-based guidelines or protocols. In particular, the long-term effects and safety of various non-pharmacological interventions, and the effectiveness and feasibility of these interventions in different age groups and different types of CHD. There is a lack of large-scale, systematic clinical trials to validate the specific effects of these non-pharmacological approaches on pain management after pediatric cardiac surgery, particularly the long-term effects, improved quality of life, and psychosocial effects compared to conventional medical treatments. In addition, there is a lack of research on individualised interventions, i.e., how non-pharmacological interventions can be tailored to each child's specific situation.

2. Purpose of the study As an emerging pain management method, non-pharmacological nursing intervention has received increasing attention worldwide, especially after cardiac surgery in children, and the cartoon-based nurse-patient interaction model has not been confirmed to be effective in postoperative analgesia in children with CHD. In this study, a cartoon-based nurse-patient interaction model was applied as a non-pharmacological pain relief method for preschool children after CHD, and its effect was observed to provide a basis for the management of postoperative pain in clinical children. The significance of the study is as follows: (1) Improve pain management effect: This study will verify whether the cartoon-based nurse-patient interaction model can effectively reduce the pain after CHD in children and improve their comfort and satisfaction, which will provide a new clinical basis for improving the

postoperative pain management practice of clinical children. (2) Optimization of treatment plans: The study will explore whether cartoon-based nurse-patient interaction models can help improve children's treatment adherence, reduce complications, stabilize hemodynamic indicators (children's heart rate, blood pressure, respiratory rate, oxygen saturation, arterial blood gases), and shorten hospital stay. These are important indicators for evaluating the merits and demerits of drug labor pain treatment regimens, and have important reference value for optimizing the treatment plan for heart disease in children. (3) Improve the psychological state of family members: The psychological state of the parents of the child directly affects the rehabilitation process of the child and the overall health of the family. Non-pharmacological nursing intervention - cartoon-based nurse-patient interaction model can effectively improve the psychological state of parents and help improve parent satisfaction. (4) Improving the quality of care: This study will also evaluate the impact of non-pharmacological nursing interventions, cartoon-based nurse-patient interaction models, on the quality of caregiver work, and explore how to improve the quality of nursing services through these interventions, thereby improving the overall satisfaction of children and caregivers. Overall, this study will not only help enrich and expand the scientific research data on the nurse-patient interaction pattern of non-pharmacological nursing intervention-cartoons, but also provide new perspectives and methods for clinical practice, especially in the special population of pediatric CHD. Through the method of empirical research, the progress of knowledge and the improvement of practice in related fields should be promoted.

3. Research design types, principles and test steps

1. Study design 1. Study design: Interventional controlled study.

2. Research Methodology:

2.1 Research subjects Children who underwent CHD surgery in the Children's Cardiac Intensive Care Unit (CCU) of Beijing Children's Hospital Affiliated to Capital Medical University from June 2024 to November 2024 were selected according to the convenient sampling method. 2.2 Grouping methodology: To ensure the ethics of the study and the feasibility of implementation. In view of the moral and interference that may arise between different non-pharmacological interventions in two groups of children in a practical clinical setting, affecting the emotions of children and health care providers, this study will adopt a phased control approach. Children in June-July 2024 were the control group and the intervention group in October-November 2024.

2.3 Sample size calculation In this study, the sample size calculation formula $N1=N2=2\times[(Z\alpha+Z\beta)\sigma/\delta]^2$ was used to estimate the sample size using the Wong-Baker scale score

as the main utility index. Consulting relevant literature [101], it was found that $\sigma=0.91$, $\delta=0.47$, the test level was $\alpha=0.05$ (two-sided), the grasp was $\beta=0.1$, and the t-cut-off value table showed $Z\alpha=1.96$ and $Z\beta=1.282$. Considering the loss to follow-up of the samples during the study, the calculated sample size was increased by 10%, and finally $N \approx 86$ was obtained, with 43 cases in each of the intervention and control groups.

2.4 Ethical principles When the sample is selected, the participants use the informed consent form to explain the purpose of the study, the process, and the version number: 1.1 Version date: 2024.7.11 4 The data collection method and the procedures of the study inform the parents of the children that this study will not cause physical or mental harm to the children and themselves, and the parents of the participants are requested to decide whether to participate in the study or not. Participants voluntarily participate and can withdraw at any time, and withdrawal has no impact on subsequent normal treatment and care. Effectively protect the privacy, respect, informed consent and other rights and interests of research subjects, and strictly keep all information obtained by participants strictly confidential. All aspects of the evaluation process will follow a standardized process to ensure consistency and accuracy in data collection. To ensure the accuracy and reliability of the information, participant feedback will be collected in a confidential environment, and the assessment process will avoid any suggestions or preconceived notions that could lead the participant to ensure their comfort and the authenticity of their responses. Additionally, we will regularly review data collection and management processes to identify and address potential issues, ensuring the reliability and validity of the study.

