2.5.3 Pre-trial In September 2024, 5 children with CHD who met the criteria for inclusion were selected at Beijing Children's Hospital Affiliated to Capital Medical University for pre-experiment to observe the feasibility of the intervention method.

3. Research period 2024.8.1-2024.12.31

4. Subject selection Inclusion criteria: (1) According to the "Guidelines for the Diagnosis and Treatment of CHD in Children" and cardiac ultrasound imaging [100] Children diagnosed with CHD for surgical treatment; (2) Age 3~7 years old, including 3 and 7 years old; (3) The surgical method is thoracotomy; (4) Diagnosis of ventricular septal defect, atrial septal defect or atrial septal defect combined with ventricular septal defect, patent ductus arteriosus, tetralogy of Fallot; Exclusion criteria: (1) Those with obvious abnormal cardiovascular lung, liver and kidney function, other chronic diseases, neuropsychiatric diseases, and malignant tumors; (2) Congenital heart disease combined with other organ malformations; (3) taking sedatives and antidepressants; (3) Those with intellectual disability, developmental delay, or behavioral disorder; (4) Hearing and communication impairments in children; (5) Parents of children with mental retardation or mental illness; Removal criteria: (1) Extubation cannot be done after surgery; (2) Unplanned reoperation 48 hours after surgery; (3) Unable to communicate normally due to impaired consciousness or changes in condition after surgery; (4) Those who stop treatment due to other reasons such as transfer to hospital, department or death midway. (5) Children and their families choose to withdraw from the study midway for

various reasons.

4. Research methods

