10. Data security monitoring All collected data will be stored and analyzed uniformly to strictly protect the privacy of participants. To ensure the accuracy of the data and the reliability of the research, we will also conduct regular audits of data quality. All reviews and entries are entered by the researcher into the same computer electronic data record form file. All questionnaires are collected and checked by the survey staff on the spot, and after the survey, the researcher reviews the collected questionnaires and eliminates invalid questionnaires.

11. Statistical processing The data were entered by excel2023 software and a database

was established, and SPSS29.0 was used to perform statistical analysis on the data. The data that meet the normal distribution are expressed by mean \pm standard deviation, and the data that do not meet the normal distribution are statistically described by the median and interquartile spacing M (IQR). The counting data are described by composition ratio and percentage. For statistical inference, paired t-tests were used for intra-group comparisons of normally distributed and homogeneous variance, and two-sample t-tests were used for comparisons between groups. The correction t-test is used for uneven variance; The counting data were tested by chi-square. All statistical tests were two-tailed tests, with a $P<0.05$ indicating that the difference was statistically significant.

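### Group and calendar phase are the same variable, and the plan's unadjusted tests would read any systematic age or diagnosis shift between phases as an intervention effect, in either direction

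*Combined protocol and SAP*

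**What the plan says.** Section 2.2 says that "this study will adopt a phased control approach" and fixes the groups by date: "Children in June-July 2024 were the control group and the intervention group in October-November 2024". There is no randomisation and no concurrent control. Its stated reason is interference between groups treated side by side. Under section 2.1 the children "were selected according to the convenient sampling method".

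The eligibility criteria (section 4, Subject selection) are common to both phases but wide: "Age 3~7 years old, including 3 and 7 years old", and "Diagnosis of ventricular septal defect, atrial septal defect or atrial septal defect combined with ventricular septal defect, patent ductus arteriosus, tetralogy of Fallot". They also require that "The surgical method is thoracotomy". There is no quota, matching or stratification by phase.

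For inference between groups, section 11 says "two-sample t-tests were used for comparisons between groups", with a corrected t-test for unequal variances, and "The counting data were tested by chi-square". No regression, covariate adjustment, propensity method or stratified analysis appears anywhere. Section 6 lists general information among the observation indicators, but no section uses it for adjustment.

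The purpose section (section 2) states a causal aim, to verify that the model reduces postoperative pain. It does not say that phase and intervention cannot be separated.

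**The concern.** The t-test estimates the difference between the October-November mean and the June-July mean. That equals the effect of the cartoon model only if the two phases would otherwise have had the same expected score. Chance imbalance in age or diagnosis is not the problem, because the t-test's standard error already covers it. The gap is a systematic difference in expected case mix. Such a difference adds one-for-one to the estimate, and a larger sample does not remove it.

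The target difference is only 0.47 points, so a modest shift can be a large share of it. Depending on direction, the trial could report a benefit that does not exist, report a harm that does not exist, or miss a real benefit.

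**Working it through.** **Inputs from the documents (section 2.3).** σ = 0.91, δ = 0.47, two-sided α = 0.05, 43 children per group.

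**The plan's own figure.** 2 × [(1.96 + 1.282) × 0.91 / 0.47]² = 78.8 per group, and 78.8 × 1.1 = 86.7. The stated 86 is therefore close to the per-group result, but section 2.3 uses it as the total. That is a separate point. I use 43 per group because that is what will be recruited; power there is 66.8% (normal approximation), not 90%.

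**How a shift enters.** If τ is the true effect, the expected unadjusted difference (intervention minus control) is

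τ + (difference in tetralogy proportion × its effect on the score) + (difference in mean age × slope per year) + any unmeasured phase effect.

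**Generic shift b, no true effect.** SE = 0.91 × √(2/43) = 0.196. The rejection rate is Φ(−1.96 + b/SE) + Φ(−1.96 − b/SE). For b = 0, 0.1, 0.2, 0.3 and 0.47 points it is 5.0%, 8.0%, 17.5%, 33.3% and 66.8%. With 87 per group, b = 0.2 gives 30.5%, so a larger trial makes the error more likely.

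**Case-mix scenarios.** Every case-mix input here is an assumption; the documents give none. Simulation: 40,000 runs per scenario, 43 per group, residual SD 0.91, age SD 1.2 years, older children scoring lower, no true effect. The intervention phase is the older one except in the reversed and opposed rows. Adjusted means linear regression on group, age and tetralogy.

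| Tetralogy, control / intervention | Tetralogy effect | Age gap | Slope per year | Bias | Unadjusted | Adjusted |
|---|---|---|---|---|---|---|
| 20% / 20% | +1 | 0 | 0.2 | 0 | 5.0% | 5.2% |
| 15% / 10% | +0.5 | 0.2 y | 0.1 | −0.05 | 5.6% | 5.0% |
| 20% / 10% | +0.5 | 0.5 y | 0.1 | −0.10 | 7.8% | 5.0% |
| 30% / 10% | +0.5 | 0.5 y | 0.1 | −0.15 | 11.4% | 5.1% |
| 20% / 10% | +1 | 0.5 y | 0.2 | −0.20 | 14.8% | 5.0% |
| 30% / 10% | +1 | 0.5 y | 0.2 | −0.30 | 27.2% | 5.1% |
| 30% / 10% | +2 | 0.5 y | 0.2 | −0.50 | 46.7% | 4.9% |
| 10% / 30% (reversed) | +1 | 0.5 y, control older | 0.2 | +0.30 | 27.3% | 5.1% |
| 30% / 10% (opposed) | +1 | 0.5 y, control older | 0.2 | −0.10 | 7.3% | 5.0% |

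In the 27.2% row the bias is 0.2 × 1 + 0.5 × 0.2 = 0.30, and 0.30 / 0.47 = 64% of the target. Nearly all of those rejections (27.1%) favour the intervention. In the reversed row nearly all (27.2%) point to harm.

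*Check by hand of the 27.2% row.* The average within-group variance is 0.91² + (0.3 × 0.7 + 0.1 × 0.9)/2 + 0.2² × 1.2² = 0.828 + 0.150 + 0.058 = 1.036, so SD = 1.02. SE = 1.02 × √(2/43) = 0.22, and 0.30 / 0.22 = 1.37. Φ(1.37 − 1.96) is about 28%, in line with the simulation.

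**Unmeasured phase shift added to the 27% scenario, still with no true effect.**

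| Unmeasured shift | Unadjusted | Adjusted |
|---|---|---|
| 0.1 SD, same direction | 41.8% | 7.0% |
| 0.2 SD, same direction | 58.1% | 13.7% |
| 0.3 SD, same direction | 73.6% | 25.2% |
| 0.2 SD, opposite direction | 8.1% | 13.8% |

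**True effect of −0.47.** In the 27% scenario the unadjusted estimate averages −0.77 and the adjusted one −0.47 (power 60.3%). In the reversed scenario the unadjusted estimate averages −0.17 with power 11.8%, and the adjusted one −0.47 with power 59.8%.

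**The case against.** The strongest objection is that the harm is conditional on two links the documents do not supply: a case-mix shift between phases, and a relation of age or diagnosis to the Wong-Baker score. The mildest scenario barely moves the error rate (5.6%). The 27% figure needs tetralogy to fall from 30% to 10% within one unit in a few months, with an age gap in the same direction. This stands as a limit on the size claimed. It does not answer the point that nothing in the plan prevents such a shift or corrects for one.

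The plan also has real safeguards: a stated reason for phasing, the same caregivers (section 2.5.2.2), the same unit and base analgesic care, and thoracotomy, exclusion and removal criteria that narrow the case mix. None of these balances age or diagnosis between phases. Describing general information by group would display an imbalance without correcting it.

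The simulation treats 0.91 as the residual SD, whereas section 2.3 uses it as the within-group SD of the score. Holding the total SD at 0.91 gives 32.7% instead of 27% and 17.0% instead of 14.8%, so the point becomes stronger.

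Finally, regression cannot undo aliasing, and with an opposing unmeasured shift it does worse than the t-test (13.8% against 8.1%). That is correct, and it is why adjustment alone is not enough. The tetralogy term would also be thinly supported: 10% of 43 is about four children. Grouping the diagnoses as tetralogy versus the rest is an analyst's choice, as the documents list them without ranking.

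**Conclusion.** The concern holds. Group and phase are identical, the sample is one of convenience, and the only planned comparisons are unadjusted, so the primary result cannot carry the causal reading in the purpose section. That conclusion follows from the text and needs no assumed numbers.

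The size of the error is not known. Across the assumed case-mix scenarios the false-positive rate runs from 5.0% to 47%, and the direction can be benefit or harm. Adjustment for age and diagnosis restores about 5% only if they are the sole confounders and the linear model is right. Unmeasured time effects remain, so the limit on interpretation must be written down as well. This should be corrected before outcomes are compared between groups.

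**What to change.** **(a) Section 11.** Make the primary between-group comparison a linear regression on group, age and diagnosis (tetralogy of Fallot versus the simple shunt lesions). Use the same Wong-Baker score that the t-test would have used. Keep the t-test as unadjusted support, and tabulate age and diagnosis by phase. The scores are taken every 4 hours (section 2.5.1.4) and the analysed time point is not defined; this needs settling for either method.

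**(b) Sections 2 (Purpose of the study) and 11.** State that phase and intervention are fully aliased and that adjustment removes only measured case mix, not unmeasured time effects. State that the result will be worded as an adjusted between-phase difference, that is, an association.

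**Cost.** Wording, plus two covariates already needed to establish eligibility; no new data. With one term for age and one for tetralogy, residual degrees of freedom fall from 86 − 2 = 84 to 86 − 4 = 82. At δ = 0.47 with 43 per group, simulated power goes from 65.6% to 64.5% if the covariates are balanced and uninformative. If they are balanced but prognostic (+1 point for tetralogy, 0.2 point per year), it rises from 56.0% to 64.7%, or from 65.7% to 77.7% with the total SD held at 0.91. Both parts are needed, because (a) alone does not make the causal reading valid.

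### The sample-size formula gives 79 per group (87 after the 10% increase), but the plan enrols 43 per group, so power under its own inputs is about 66%, not 90%

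*Combined protocol and SAP*

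**What the plan says.** Section 2.3 (Sample size calculation) takes the Wong-Baker score as the main index and uses the formula "N1=N2=2\times[(Z\alpha+Z\beta)\sigma/\delta]^2". The inputs are "\sigma=0.91$, $\delta=0.47", taken from a cited source. The error rates are given as "the test level was $\alpha=0.05$ (two-sided), the grasp was $\beta=0.1", with normal quantiles "Z\alpha=1.96$ and $Z\beta=1.282". The result is raised by 10% for loss to follow-up, and the section ends: "finally $N \approx 86$ was obtained, with 43 cases in each of the intervention and control groups".

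Two other sections bear on how the formula must be read. Section 2.2 makes the groups separate cohorts: control children from June–July 2024 and intervention children from October–November 2024. Section 11 compares the groups with two-sample t-tests, all two-tailed at P < 0.05.

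**The concern.** A formula headed N1=N2 returns the number needed in each group. The leading factor 2 is the usual term for the variance of a difference between two independent means. The plan's final figure of 86 looks like that per-group number, yet it is presented as the total for both groups.

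If so, each group has half the children the calculation requires and the stated β = 0.1 does not describe the design. This is the only sample-size justification in the document, and it concerns the main index. A reader who relied on 90% power would give a non-significant result more weight against the intervention than the trial can support.

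**Working it through.** **Inputs, all from section 2.3:** Zα = 1.96, Zβ = 1.282, σ = 0.91, δ = 0.47, a 10% increase, and a stated result of 86 in total, 43 per group. The test, a two-sided two-sample t-test, is from section 11.

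**1. The formula as printed**

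- (Zα + Zβ)σ/δ = (1.96 + 1.282) × 0.91 / 0.47 = 6.277
- 6.277² = 39.40
- n per group = 2 × 39.40 = 78.80, rounded up to 79
- After the increase: 78.80 × 1.10 = 86.68 per group, rounded up to 87
- Total: 2 × 87 = 174

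The number 86 is therefore recovered, apart from rounding, only as the size of one group. As a total it does not reproduce: 2 × 86.68 = 173.4.

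**2. Could other settings give 43 per group?**

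| Variant | n per group | After +10% |
|---|---|---|
| As printed | 78.8 | 86.7 |
| One-sided α = 0.05 | 64.2 | 70.7 |
| 80% power | 58.9 | 64.8 |
| Factor 2 omitted | 39.4 | 43.3 |

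Only omitting the factor 2 gives 43. That is a one-sample or paired formula. It agrees neither with the printed formula nor with the comparison of two separate cohorts by a two-sample test.

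**3. Power of the design as stated**

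The standardised difference is 0.47/0.91 = 0.5165. The t-test with n per group has 2n − 2 degrees of freedom and noncentrality 0.5165 × √(n/2). For n = 43 the noncentrality is 2.395 with 84 degrees of freedom. For n = 39 it is 2.281 with 76. The figure of 39 is 43 less about 10% (43 × 0.9 = 38.7).

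| n per group | Power, t-test | Power, normal approximation |
|---|---|---|
| 39 | 61.5% | 62.6% |
| 43 | 65.8% | 66.8% |
| 79 | 89.7% | 90.1% |
| 87 | 92.3% | 92.6% |

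The type II error is 34.2% at 43 per group and 38.5% at 39, against the stated 10%.

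**4. Difference detectable with 90% power (t-test, σ = 0.91)**

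- 43 per group: 0.644 points
- 39 per group: 0.677 points

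These are 1.37 and 1.44 times the planned 0.47 (0.644/0.47 and 0.677/0.47).

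**The case against.** The arithmetic cannot be answered, but several limits on the claim are fair.

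- **How the slip arose is not shown.** The section prints no intermediate step. Halving the per-group figure requires 86.68 to have been cut down to 86. Omitting the factor 2 gives 43.3, which rounds to 43 and doubles to 86 more naturally. This stands, but it changes nothing: either way each group is half what the printed formula requires, and power at 43 per group is the same.
- **87 is what the plan's normal-theory formula returns, not an exact t-test requirement.** By the t-test, 79 evaluable children per group give 89.7% power and 80 give 90.1%. Protecting 80 against 10% loss means 88 enrolled per group (80 × 1.1) or 89 (80/0.9 = 88.9). This stands as a refinement of one or two children per group.
- **The power figures depend on σ and δ from a source not examined here.** Pain is scored every 4 hours (section 2.5.1.4), and the plan does not say which time point or summary σ describes. A summary over several scores might be more precise. However, section 11 names no such summary, no repeated-measures model and no baseline adjustment, and the calculation takes no credit for them. The 66% is therefore conditional on the plan's own inputs, as is its claim of 90%.
- **Nothing in the document says how a null result would be read, or that 43 per group is the most that can be recruited.** Both points are right. The consequence that can be supported is the larger type II error.

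**Conclusion.** The concern holds. With the plan's own formula and inputs, the requirement is 79 children per group, or 87 after the 10% increase (174 in total). The plan provides 43 per group, 86 in total.

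Taking σ = 0.91 and δ = 0.47 as given, and the two-sided two-sample t-test of section 11, power is 65.8% with all 43 per group and 61.5% with 39. The risk of missing the planned effect is more than three times the stated 10%. The gap between 86 and 87 is rounding, and the finding does not rest on it. The formula, inputs and result are all legible, and no other section corrects the figure.

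**What to change.** Correct section 2.3 so that the formula, the inputs and the group sizes agree. First state that the formula gives 79 per group, 87 after the 10% increase. Then take one of two routes:

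- **Keep 90% power.** Replace 43 with 87 per group (174 in total). If the t-test is to keep 90% power after 10% loss, use 88 or 89 per group. This roughly doubles recruitment, and the two enrolment windows in section 2.2 would have to accommodate it.
- **Keep 43 per group.** Withdraw β = 0.1 for this size. State that power for a difference of 0.47 is about 66%, or about 61% after 10% loss, or equivalently that 90% power holds only for a difference of about 0.64 to 0.68 points. The sponsor should also say why 43 was retained, since the document gives no accrual limit. This costs only rewording, but it makes the claim accurate without improving the power.

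If enrolment is already complete, the second route still applies, and the corrected statement should be carried into the report. Power recalculated from the observed data would not be a substitute.

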4.1.3 Postoperative pain management: On the basis of postoperative pain management in the control group, the responsible nurse uses a mobile phone or Ipad to play the cartoons selected by the child before surgery according to the child's choice, and can watch the cartoon throughout the whole process or according to the child's wishes after waking up after the operation, and the volume of the device is adjusted to a comfortable

level, each cartoon does not exceed 30 minutes, 3~6 times a day, to distract attention and let the child's eyes rest to protect vision. Nurses can also discuss the plot with the child, mobilize the child's subjective initiative, gain their trust, and change from passive participation to active participation.

5. Concomitant medication None

6. Observation indicators General information, physiological indicators, postoperative complications, pain assessment, children's anxiety assessment (mYPAS score), anxiety assessment, parent satisfaction.

7. Pre-assessment of project risks and risk disposal plan In this study, the use of electronic products such as mobile phones or IPAPs may cause visual fatigue and dependence in children.

8. Quality control and quality assurance of research The quality control and supervision of research are explained from the aspects of laboratory index testing, implementation of relevant SOPs, researcher training, subject compliance, and research monitoring.

8.1 Researcher training Nursing is carried out by the same group of caregivers as the control group, but before the intervention group implements the study, the researcher completes the implementation plan and data collection method training of the cartoon-based nurse-patient interaction model during the interval.

8.2 Subject compliance Before participating in the trial, the investigator should explain the potential risks of using this study to all subject guardians and inform the subjects that cooperating with the safety monitoring required in the trial protocol can minimize the risks.

9. Data preservation The collected research data is entered on the same day, and the researcher enters it by one person, with double data entry and regular data cleaning to minimize human error. At the same time, use a secure, encrypted electronic data system to protect participant information.

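### Section 2.4 has parents told without qualification that the study causes no harm, although section 7 names two possible harms of the viewing device and section 8.2 requires risks to be explained

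*Combined protocol and SAP*

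**What the plan says.** Four places in the combined protocol and SAP bear on this.

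- **Section 2.4, Ethical principles.** The study is to "inform the parents of the children that this study will not cause physical or mental harm to the children and themselves". No qualifier is attached. The sentence continues: "the parents of the participants are requested to decide whether to participate in the study or not". The assurance is thus part of what the protocol describes as being said when participation is decided.
- **Section 7, risk pre-assessment.** The section states that "the use of electronic products such as mobile phones or IPAPs may cause visual fatigue and dependence in children". Read with section 4.1.3, the garbled device name evidently means tablets.
- **Section 4.1.3, postoperative pain management in the intervention group.** The viewing pattern is given as "each cartoon does not exceed 30 minutes, 3~6 times a day, to distract attention and let the child's eyes rest to protect vision".
- **Section 8.2, Subject compliance.** Before participation, "the investigator should explain the potential risks of using this study to all subject guardians". The section adds that cooperating with safety monitoring can minimise the risks.

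**The concern.** The protocol gives two incompatible accounts of risk. In one, parents hear that there is no harm of either kind. In the other, the investigator explains risks, and section 7 says what they are.

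The participants are 3 to 7 years old and have had a thoracotomy (section 4, Subject selection), and under 2.4 their parents decide for them. Accurate risk information to parents is therefore a central consent safeguard. Staff who took 2.4 literally would give guardians of intervention children a statement that the protocol contradicts. What is at stake is the accuracy of consent information, not the validity of the treatment comparison.

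**Working it through.** No formula or stated figure is involved. The check is a comparison of the passages, followed by a count of the children concerned.

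**Step 1: is the assurance absolute?** Yes. Section 2.4 says the study will not cause harm. It does not say that harm is unlikely or minor. It covers physical and mental harm, to children and to parents.

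**Step 2: does section 7 contradict it?** Yes, for the children.

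| Category excluded in 2.4 | Effect named in section 7 |
|---|---|
| Physical harm | Visual fatigue |
| Mental harm | Dependence (mental or behavioural) |

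Both named effects fall in a category that 2.4 rules out. Section 7 says only that they may occur, but a possible effect is enough to make an unconditional denial inaccurate. Section 7 names no effect on parents, so that part of the assurance is not contradicted.

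**Step 3: did the authors treat the eye risk as real?** Yes. Section 4.1.3 gives protection of vision as a reason for limiting each viewing. Taken at its stated figures, the daily ceiling runs from 3 × 30 = 90 minutes to 6 × 30 = 180 minutes. This shows only that the exposure section 7 refers to is a planned part of the intervention.

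**Step 4: does section 8.2 resolve it?** No. It presupposes that there are risks and requires them to be explained to all guardians. That provides a second route to disclosure, but it also conflicts with 2.4, and nothing says which instruction governs.

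**Step 5: whom does it concern?** The device belongs to the intervention only.

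- Intervention group: 43 planned (section 2.3).
- Pre-trial: 5 children (section 2.5.3). The stated aim was to observe feasibility of the intervention, but the text does not say outright that cartoons were shown, so these count only if they were.
- Control group: 43 planned, given routine care without the device. Section 7 does not contradict the assurance for them.

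The range is 43 to 43 + 5 = 48 children.

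**Step 6: is a planned harm estimate affected?** None is visible. The observation indicators in section 6 name neither visual fatigue nor dependence, and list no harm measure reported by parents.

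**The case against.** The strongest reply is that disclosure is already required. Section 8.2 has the investigator explain potential risks to all guardians, so 2.4 is not the only information they receive. A site could give a general reassurance and still describe the two effects. That would be poor wording, but it would not be concealment. This stands as a limit on the consequence. It does not make the sentence in 2.4 accurate.

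Second, section 2.4 makes the informed consent form the vehicle for explaining the study, and the consent pages were not in the material available. The form may list both risks correctly. This also stands, and it confines the point to protocol wording.

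Third, the effects are hedged and appear mild, and 4.1.3 contains a measure aimed at one of them. That is true and lowers the severity, but mild risks still need to be described correctly.

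Fourth, a page footer interrupts the sentence in 2.4, so it should not be read as a word-for-word script. That is reasonable, but the clause stating the assurance is intact.

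A reader might also infer more than the documents support:

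- *That guardians actually consented on false information.* This cannot be established without the form, and 8.2 provides for the opposite.
- *That every guardian in the study was misinformed.* Control children are not assigned the device.
- *That parents reassured in this way would under-report, biasing harm results towards zero.* Section 6 contains no measure of these effects that could be biased. No passage makes parents the best-placed observers: after surgery it is the responsible nurse who plays the cartoons. Any effect on reporting is conjecture.

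**Conclusion.** The point holds as a contradiction in the protocol's wording. The unqualified assurance in 2.4 is wrong as written for guardians of children given the device: 43 planned, or up to 48 if the pre-trial children were shown cartoons. Section 8.2 reduces the practical consequence without removing the conflict.

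The conclusion rests on two readings: that visual fatigue counts as a physical effect and dependence as a mental or behavioural one, and that 2.4 describes what parents are meant to hear. The mismatch can be verified by reading the sections together. What any guardian was actually told cannot be verified.

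This should be fixed, because it concerns what guardians of young children are told at consent and costs very little to correct. It is not a must-fix: disclosure is required elsewhere, the named effects appear mild, and allocation, sample size, the primary analysis and any planned harm estimate are untouched.

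**What to change.** 1. In section 2.4, delete the assurance that the study causes no physical or mental harm.
2. In its place, state the risks section 7 already names: that device use may cause visual fatigue and dependence. The right to withdraw at any time is already in 2.4 and needs no change.
3. Reconcile 2.4, 7 and 8.2 so that all three describe the same risks and 2.4 refers to the explanation that 8.2 requires.
4. Compare the consent form with the corrected text. If it already states the two risks and carries no assurance of no harm, nothing further is needed. If it carried the no-harm wording, re-inform the guardians of children given the device, including pre-trial children if they were shown cartoons.

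The cost is a short edit to the protocol (and to the form if it repeats the assurance) and an ethics notification. A few parents may ask more questions or decline. The documents give no basis for estimating how many.
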